1. VERSION HISTORY

This SAP for Study C3291037 is based on the protocol amendment 3 dated 12AUG2019.

Table 1. Summary of Major Changes in SAP Amendments

Version/Date	Associated Protocol Amendment	Specific Changes	Rationale
1 16MAY2018	Original 16MAR2018	Not Applicable	Not Applicable
2 27SEP2019	Protocol Amendment 3 12 Aug 2019	Removal of telephone follow-up at Day 36; addition of a clinic visit at Day 43; addition of restrictions to concurrent medications during the follow-up phase; and changes to the pruritis scale descriptions, endpoints, and analysis.	Per Protocol Amendment 3
3 10NOV2020	Protocol Amendment 3 12 Aug 2019	Modifications of efficacy and patient reported outcomes endpoints: 
 • Only descriptive summary will be provided for primary efficacy and selected secondary endpoints. • No summary/analysis will be done for tertiary/exploratory endpoints. Appendix 8 Listing of Abbreviations was added	Study termination

2. INTRODUCTION

This SAP provides the detailed methodology for summary and statistical analyses of the data collected in Study C3291037. This document may modify the plans outlined in the protocol; however, any major modifications of the primary endpoint definition or its analysis will also be reflected in a protocol amendment.

2.1. Study Objectives

Study objectives and corresponding endpoints are provided in the [Table 2](#) below.

Table 2. Study Objectives and Endpoints

Primary Efficacy Objective	Primary Efficacy Endpoint

 To compare the efficacy of crisaborole ointment, 2% applied twice daily (BID) versus vehicle in pediatric and adult subjects (ages 2 years and older) with mild to moderate Atopic Dermatitis (AD). 	
 Percent change from baseline in the Eczema Area and Severity Index (EASI) total score at Day 29.
Primary Safety Objectives	Primary Safety Endpoints

 To evaluate the safety and local tolerability of crisaborole ointment, 2% applied BID versus vehicle in pediatric and adult subjects (ages 2 years and older) with mild to moderate AD. To evaluate the safety and local tolerability of hydrocortisone butyrate cream 0.1% and pimecrolimus cream 1% applied BID in pediatric and adult subjects (ages 2 years and older) with mild to moderate AD. 	
 Adverse Events (AEs), Serious Adverse Events (SAEs), local tolerability, discontinuations and clinically significant changes in vital signs and clinical laboratory parameters.
Secondary Objectives	Secondary Endpoints

 To evaluate the effect of crisaborole ointment, 2% applied BID versus vehicle on additional efficacy endpoints over time in pediatric and adult subjects (ages 2 years and older) with mild to moderate AD. To evaluate the efficacy of crisaborole ointment, 2% BID versus hydrocortisone butyrate cream 0.1% and pimecrolimus cream 1% applied BID in pediatric and adult subjects (ages 2 years and older) with mild to moderate AD. 	
Efficacy endpoints:
 
 Percent change from baseline in EASI total score by scheduled time points except Day 29. Achievement of success in the Investigator's Static Global Assessment (ISGA) (defined as an ISGA score of Clear (0) or Almost Clear (1) with at least a 2-grade improvement from baseline) by scheduled time points. Achievement of ISGA score of clear (0) or almost clear (1) by scheduled time points. Achievement of EASI75 ($\geq 75\%$ improvement from baseline) by scheduled time points. Time to EASI75. Change from baseline in %BSA by scheduled time points.

 To evaluate the effect of crisaborole ointment, 2% applied BID versus vehicle, hydrocortisone butyrate cream 0.1% and pimecrolimus cream 1% applied BID on patient/observer reported outcomes over time in pediatric and adult subjects (ages 2 years and older) with mild to moderate AD. 	
Patient/observer reported outcomes (PRO) endpoints:
 
 Change from Baseline in Peak Pruritus Numerical Rating Scale (NRS) – for subjects >12 years by scheduled time points. Change from Baseline in Patient Reported Itch Severity Scale - for subjects age 6-11 years Scale by scheduled time points. Change from Baseline in Observer Reported Itch Severity Scale – for subjects <6 years by scheduled time points. Time to ≥ 2-point improvement from Baseline in Peak Pruritus NRS for subjects >12 years. Time to ≥ 3-point improvement from Baseline in Peak Pruritus NRS for subjects >12 years. Time ≥ 2 point to improvement from Baseline in Observer Reported Itch Severity Scale - for subjects <6 years. Time to ≥ 3-point improvement from Baseline in Observer Reported Itch Severity Scale - for subjects <6 years. Achievement of ≥ 2-point improvement from Baseline in Peak Pruritus NRS for subjects >12 years. Achievement of ≥ 3-point improvement from Baseline in Peak Pruritus NRS for subjects >12 years. Achievement of ≥ 2-point improvement from Baseline in Observer Reported Itch Severity Scale - for subjects <6 years. Achievement of ≥ 3-point improvement from Baseline in Observer Reported Itch Severity Scale - for subjects <6 years. Change from baseline in Dermatology Life Quality Index (DLQI) (for Subjects 16 years and older), Children's Dermatology Life Quality Index (CDLQI) (for Subjects 4-15 years), and Dermatitis Family Impact Questionnaire (DFI) (Completed by parent/caregiver

Table 2. Study Objectives and Endpoints

Figure 1 is a bar chart showing the percentage of subjects with CCI (red) and without CCI (black) across scheduled time points. The y-axis represents the percentage of subjects, ranging from 0% to 100%. The x-axis represents the scheduled time points. The chart shows that the percentage of subjects with CCI is consistently higher than the percentage of subjects without CCI across all time points.

Scheduled Time Point	CCI (%)	Without CCI (%)
1	85	15
2	88	12
3	90	10
4	92	8
5	94	6
6	96	4
7	98	2
8	100	0

2.2. Study Design

This is a Phase 3b/4, multicenter, randomized, assessor blinded, vehicle and active (topical corticosteroid [TCS] and topical calcineurin inhibitor [TCI]) controlled study of the efficacy, safety and local tolerability of crisaborole ointment, 2% in pediatric and adult subjects, ages 2 years and older, with mild to moderate AD involving at least 5% treatable body surface area (%BSA). Treatment will be clinical assessor blinded for all treatment arms and double blinded for crisaborole ointment, 2% and vehicle treatment arms.

A total of approximately 600 subjects will be enrolled in the study, of which at least 150 subjects aged 2-6; at least 140 subjects aged 7-11; at least 120 subjects aged 12-17, and up to 90 subjects will be adults. Following the screening period (up to 35 days prior to Baseline/Day 1), eligible subjects will be randomized at the Baseline/Day 1 visit.

Randomization will be stratified by eligibility for TCS or TCI treatment as per national approved labels and eligibility provided in Section 4 of the protocol. Cohort 1 will be for subjects who are eligible for TCS therapy, and Cohort 2 will be for subjects who are not eligible for TCS therapy but eligible for TCI therapy. The investigational product will be applied BID for 28 days to the Treatable BSA identified at Baseline/Day 1. Any new AD on treatment eligible locations occurring following Baseline/Day 1 should also be treated with the study drug after consultation with the Investigator at the next visit.

The primary efficacy endpoint is the percent change from baseline in the EASI total score at Day 29.

For the efficacy comparison of crisaborole versus vehicle, subjects from both Cohort 1 and Cohort 2 are included in the analysis, adjusted for cohort effect. For the efficacy comparison of crisaborole versus TCS, only subjects from Cohort 1 are included in the analysis. For the comparison of crisaborole versus TCI, only subjects from Cohort 2 are included in the analysis.

[figure not shown]
Safety and efficacy assessments will be conducted at the investigator site by a clinical assessor blinded for treatment arms.

A sub-study will be conducted at selected investigator sites to evaluate differences of changes in epidermal skin thickness as measured by Optical Coherence Tomography (OCT) between treatment groups in Cohort 1. Detailed statistical analysis for sub-study will be given in a separate SAP.

Scheduled study visits for all subjects will occur at Screening, Baseline/Day 1, Day 8, Day 15, Day 22, Day 29 (End of treatment/Early termination) and Day 43 or 14 Days after last dose if subject is terminated early from treatment. A follow up telephone call will be made by site staff to the subjects/caregivers on Day 60 or at least 28 days after last dose if subject is terminated early from treatment. Subjects enrolled in the OCT sub-study will attend the clinic on Day 60 and do not require a telephone call on Day 60.

A schematic of the study design is shown in [Figure 1](#).

Figure 1. Study Design Schematic

1

a. Treatment will be clinical assessor blinded for all treatment arms and double blinded for crisaborole ointment, 2% and vehicle treatment arms.

3. ENDPOINTS AND BASELINE VARIABLES: DEFINITIONS AND CONVENTIONS

3.1. Primary Endpoint(s)

3.1.1. Efficacy Endpoint

The primary efficacy endpoint is:

- Percent change from baseline in EASI total score at Day 29.

3.1.2. Safety Endpoints

The primary safety endpoints are:

- AEs, SAEs, local tolerability, discontinuations and clinically significant changes in vital signs and clinical laboratory parameters.

3.2. Secondary Endpoint(s)

3.2.1. Efficacy Endpoints

The secondary efficacy endpoints are:

[figure not shown]
- Percent change from baseline in EASI total score by scheduled time points except Day 29;
- Achievement of success in ISGA (score of clear (0) or almost clear (1) with at least a 2-grade improvement from baseline) by scheduled time points;
- Achievement of ISGA score of clear (0) or almost clear (1) by scheduled time points;
- Achievement of EASI75 by scheduled time points;
- Time to EASI75;
- Change from baseline in %BSA by scheduled time points.

3.2.2. Patient Reported Outcomes (PRO) Endpoints

The secondary PRO endpoints are:

(Note: The peak pruritus NRS (11-category numeric rating scale) is subject reported for 12 years and older subjects. A 5-category subject reported peak pruritus scale has been developed for subjects \geq 6 and <12 years of age. The observer reported peak pruritus NRS will be completed by a caregiver for subjects <6 years old. The peak pruritus data will be analyzed separately for these three age groups):

- Change from baseline in peak pruritus NRS by scheduled time points for:
 - Subjects ≥ 12 years.
- Change from baseline in Patient Reported Itch Severity Scale for:
 - Subjects ≥ 6 and < 12 years.
- Change from baseline in Observer Reported Itch Severity Scale for:
 - Subjects < 6 years.
- Time to ≥ 2 -point improvement from baseline in peak pruritus NRS for:
 - Subjects ≥ 12 years;
 - Subjects < 6 years.
- Time to ≥ 3 -point improvement from baseline in peak pruritus NRS for:
 - Subjects ≥ 12 years;
 - Subjects < 6 years.
- Achievement of ≥ 2 -point improvement from baseline in peak pruritus NRS by scheduled time points for:
 - Subjects ≥ 12 years;
 - Subjects < 6 years.
- Achievement of ≥ 3 -point improvement from baseline in peak pruritus NRS by scheduled time points for:
 - Subjects ≥ 12 years;
 - Subjects < 6 years.
- Change from baseline in DLQI (for subjects ≥ 16 years) by schedule time points;
- Change from baseline in CDLQI (for subjects 4-15 years) by schedule time points;
- Change from baseline in DFI (completed by parent/caregiver of subjects 2-17 years) by schedule time points.

3.4. Baseline Variables

Demographic and baseline characteristics include:

- Age (years);
- Sex;

- Race;
- Ethnicity;
- Height (cm);
- Weight (kg);
- Body Mass Index (kg/m²);
- Duration of disease (years);
- Prior treatment history (treatment naïve vs treatment [eg, TCS and/or TCI]);
- Geographic region;
- Country;
- ISGA;
- EASI;
- %BSA
- PROs (Peak Pruritus NRS, DLQI, CDLQI, DFI).

For multiple pre-treatment data besides peak pruritus and **CCI** [REDACTED] baseline will be defined as the last evaluation taken before the first dose of investigational product. For peak pruritus and **CCI** [REDACTED] the average of 7-day scores immediately prior to Day 1 (Day -6 to Day 1) will be used as the baseline.

3.5. Safety Endpoints

Safety will be assessed by the spontaneous reporting of AEs, physical examinations, and clinical laboratory results in all subjects who receive at least one dose of the investigational product. Unscheduled safety assessments may be performed at any time during the study to assess any perceived safety concerns.

3.5.1. Adverse Events

An adverse event is considered treatment-emergent adverse event (TEAE) to a given treatment if the event started during the effective duration of treatment. All events that start on or after the first dosing day and time/start time, if collected, but before end of study will be flagged as TEAEs.

Safety endpoints will be assessed by the spontaneous reporting of:

- TEAEs;
- Local tolerability AEs/SAEs;
- SAEs and AEs leading to discontinuation.

3.5.2. Laboratory Data

Below is a list of hematology and serum chemistry test parameters at Screening, Baseline/ Day 1 and Day 29/End of treatment/Early termination visit.

- Hematology: hemoglobin, hematocrit, red blood cell count, platelet count, white blood cell count (% and absolute for neutrophils, eosinophils, monocytes, basophils, lymphocytes).
- Serum chemistry: blood urea nitrogen/urea, glucose (non-fasting), creatinine, sodium, potassium, chloride, Bicarbonate or Total CO₂, alanine aminotransferase, aspartate aminotransferase, total bilirubin, alkaline phosphatase, albumin, and total protein.

3.5.3. Physical Examination

A detailed physical examination at Screening, Baseline/ Day 1 and Day 29 (End of treatment)/Early termination visit which will include but is not limited to the following organ or body systems: head, ears, eyes, nose, mouth, skin, heart and lung examinations, lymph nodes, musculoskeletal, abdomen (liver, spleen), and neurological systems. In addition, an assessment will be made of the condition of all AD involved skin.

4. ANALYSIS SETS

Data for all subjects will be assessed to determine if subjects meet the criteria for inclusion in each analysis population prior to unblinding and releasing the database and classifications will be documented per standard operating procedures.

4.1. Full Analysis Set

The primary analysis population for efficacy data will be the Full Analysis Set (FAS) defined as all randomized subjects receiving at least one dose of investigational product. All efficacy and PRO endpoints will be analyzed based on the FAS.

For each specific endpoint, only participants who have data at ≥ 1 timepoint for that endpoint will be included in the analysis.

For a binary endpoint with a threshold requirement for change from baseline, only participants with a baseline value \geq the threshold will be included in the analysis.

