6.5. Subject Withdrawal/Early Termination

Withdrawal of Investigational Product:

- If signs and symptoms of hypersensitivity are attributable to the investigational product, including contact urticaria, it must be discontinued immediately and appropriate therapy initiated.

The subject will remain in the study and continue to be followed for protocol specified follow-up procedures, unless they have withdrawn consent. If consent is withdrawn for the follow-up period, the procedures for withdrawal of consent will be followed.

Withdrawal of consent:

Subjects and/or parent/legal guardian/legally acceptable representative who request to discontinue receipt of study treatment will remain in the study and must continue to be followed for protocol specified follow-up procedures. The only exception to this is when a subject specifically withdraws consent for any further contact with him or her or persons previously authorized by the subject to provide this information. Subjects should notify the investigator in writing of the decision to withdraw consent from future follow-up, whenever possible. The withdrawal of consent should be explained in detail in the medical records by the investigator, as to whether the withdrawal is only from further receipt of investigational product or also from study procedures and/or posttreatment study follow-up, and entered on the appropriate CRF page.

Lost to follow-up:

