9.2. Efficacy Analysis

9.2.1. Analysis Sets

The primary analysis population for efficacy data will be the Full Analysis Set (FAS) defined as all randomized subjects receiving at least one dose of investigational product. The primary efficacy endpoint will also be analyzed for the Per-Protocol Analysis Set (PPAS) defined as a subset of FAS who had no protocol violations affecting the efficacy endpoints. The subjects excluded from the PPAS will be determined and documented before the study is unblinded. For all analyses, baseline value will be based on observations collected pre-dose.

For the comparison of crisaborole versus vehicle, subjects from both Cohort 1 and Cohort 2 are included in the analysis, and effect of Cohort will be adjusted. For the comparison of crisaborole versus TCS, only subjects from Cohort 1 are included in the analysis. For the comparison of crisaborole versus TCI, only subjects from Cohort 2 are included in the analysis.

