5.1. Hypotheses and Decision Rules

This study was terminated. The termination decision was made for business reasons only and was not related to any safety or efficacy concerns regarding crisaborole. Only 40% of planned participants were enrolled at termination. Due to small sample size, no hypotheses testing and decision rules. No statistical analysis and comparison will be performed. Only descriptive summary will be generated for safety data and some efficacy endpoints.

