5.2. General Methods

In general, number and percent will be presented for binary and categorical variables. Number, mean, standard deviation, standard error of the mean, median, minimum, and maximum will be presented for continuous variables. In addition, graphics may be used to present the data – specific details will be outlined in the study List of Table (LOT).

Descriptive statistics will be provided for:

- Crisaborole ointment, 2% applied BID (Cohort 1);
- Crisaborole ointment, 2% applied BID (Cohort 2);
- Crisaborole ointment, 2% applied BID (combined Cohorts 1 and 2);
- Vehicle (combined Cohorts 1 and 2);
- Hydrocortisone butyrate cream, 0.1% BID (TCS, Cohort 1);
- Pimecrolimus cream, 1% BID (TCI, Cohort 2);
- Total – only for disposition, evaluation, demographic and baseline characteristics.

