5.3.1. Binary Endpoints

For binary endpoints analyzed at each scheduled visit separately, if a subject has no data for a binary endpoint at a scheduled visit, this subject will be classified as a non-responder (NR) for that endpoint at that visit.

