6.1.2. Percent Change from Day 29 to Day 43 in EASI

Descriptive statistics will be provided for observed percent change from Day 29 to Day 43 in EASI.

6.1.3. ISGA of Success at Days 8, 15, 22, and 29

Achievement of success in the ISGA (defined as an ISGA score of clear (0) or almost clear (1) with at least a 2-grade improvement from baseline) at Days 8, 15, 22, and 29 will be summarized. Missing data will be classified as non-responder.

6.1.4. ISGA of Clear or Almost Clear at Days 8, 15, 22, and 29

Achievement of ISGA of clear (0) or almost clear (1) at Days 8, 15, 22, and 29 will be summarized. Missing data will be classified as non-responder.

6.1.5. EASI75 at Days 8, 15, 22, and 29

Achievement of EASI75 at Days 8, 15, 22, and 29 will be summarized. Missing data will be classified as non-responder. Graph depicting proportions will be provided.

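### Does SAP 4.1 leave open whether a dosed subject who is never reassessed counts as a non-responder or leaves the responder denominators?

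*SAP*

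**What the plan says.** SAP 4.1 and Protocol 9.2.1 define the Full Analysis Set (FAS) in the same way: "defined as all randomized subjects receiving at least one dose of investigational product". SAP 4.1 adds that "All efficacy and PRO endpoints will be analyzed based on the FAS". It then restricts each endpoint: "For each specific endpoint, only participants who have data at" one or more timepoints for that endpoint are included. Protocol 9.2.1 has no such restriction.

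SAP 5.3.1 deals with missed visits on binary endpoints. If a subject has no value at a scheduled visit, "this subject will be classified as a non-responder (NR) for that endpoint at that visit". SAP 6.1.5 applies this to EASI75: "Achievement of EASI75 at Days 8, 15, 22, and 29 will be summarized. Missing data will be classified as non-responder". Sections 6.1.3 and 6.1.4 do the same for the two ISGA endpoints, and 6.2.4 and 6.2.5 for the itch responders. None of them states a denominator.

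The setting is descriptive. SAP 5.1 records that "Only 40% of planned participants were enrolled at termination" and rules out testing and comparison. SAP 5.2 and 5.2.1 call for number and percentage for binary variables.

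**The concern.** The word timepoint in SAP 4.1 is not qualified, and it can be read in two ways.

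- **Baseline counts.** An ISGA of 2 or 3 at baseline is an entry criterion (Protocol 4.1.1), and EASI is scored before the first dose (Protocol 6.4.1). Practically every dosed subject then has data, and one who is never seen again is a non-responder at Days 8, 15, 22 and 29.
- **Only post-baseline data count.** The same subject leaves the denominators for ISGA success, ISGA clear or almost clear, EASI75 and the itch responders. The non-responder rule never reaches that subject, and the set is narrower than the protocol FAS.

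Nothing is tested, so the printed counts and percentages are the result for these endpoints. Two programmers could print different percentages from the same text. Dropping subjects raises the rate in any arm that has such subjects. If early losses differed between arms, the apparent gap between the arms would shift.

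**Working it through.** **Reading the text.** SAP 4.1 asks for data for the endpoint in question. EASI75 and ISGA success are defined by change from baseline, so they have no value at baseline. SAP 6.1.3 to 6.1.5 summarise the ISGA and EASI75 responders only at Days 8 to 29. If baseline counted, the restriction would remove almost nobody for ISGA or EASI. Post-baseline is therefore the natural reading, although this is inference. The two sections then run in order: 4.1 fixes who is in, and 5.3.1 assigns non-response to missed visits among those subjects.

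**Who is affected.** Only dosed subjects with no later assessment at all. Protocol 6.5 says that those who ask to stop treatment "will remain in the study and must continue to be followed for protocol specified follow-up procedures", unless they also withdraw consent to further contact. SAP Appendix 1 assigns an assessment on Days 2 to 11 to the Day 8 window.

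**Size.** The plan gives no figure on this point, so this is an illustration.

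Inputs:
- Planned sizes (Protocol 9.1): 150 in each pooled crisaborole and vehicle arm, and 75 on crisaborole per cohort.
- Enrolment (SAP 5.1): 40% of plan. This gives 0.40 × 150 = 60 and 0.40 × 75 = 30, assuming that the planned ratios held.
- Pooled Phase 3 ISGA response (Protocol 9.1): 32.1% and 21.8%. This gives 0.321 × 60 ≈ 19 responders, 0.218 × 60 ≈ 13, and 0.321 × 30 ≈ 10.
- Number never reassessed, m: not in the documents. Values of 1, 3 and 6 are assumed (1 and 3 for the single-cohort column).

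With R responders among n subjects, the rate is R/n if the never-reassessed count as failures and R/(n − m) if they are dropped. The ratio of the two is 1/(1 − m/n).

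| Column | m = 0, or counted as failures | drop 1 | drop 3 | drop 6 |
|---|---|---|---|---|
| Crisaborole, pooled | 19/60 = 31.7% | 19/59 = 32.2% | 19/57 = 33.3% | 19/54 = 35.2% |
| Vehicle, pooled | 13/60 = 21.7% | 13/59 = 22.0% | 13/57 = 22.8% | 13/54 = 24.1% |
| Crisaborole, one cohort | 10/30 = 33.3% | 10/29 = 34.5% | 10/27 = 37.0% | – |

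Binomial standard errors, √(p(1 − p)/n):
- 19/60: √(0.317 × 0.683/60) = 6.0 points.
- 10/30: √(0.333 × 0.667/30) = 8.6 points.

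Dropping 3 moves these rates by 1.7 and 3.7 points, well inside one standard error. Dropping 6 of 60 moves the pooled crisaborole rate by 3.5 points, also inside one.

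Difference between the pooled arms:
- None dropped: 31.7 − 21.7 = 10.0 points.
- 3 dropped in each arm: 10.5.
- 3 dropped on crisaborole only: 11.7.
- 3 dropped on vehicle only: 8.9.

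The SAP does not produce this difference.

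**Recovering the denominator.** The responder count is the same under both readings, and count and percentage are both reported. A cell showing 19 (33.3%) implies 57 subjects; 19 (31.7%) implies 60.

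**The case for a change.** The best case for a change is that the percentage is all a reader gets, so its denominator should be fixed in writing. SAP 4 itself wants membership of the analysis populations settled before unblinding. If exclusion is intended, the subjects with the least data escape the rule that missing means non-response, and the SAP should say so and count them. If it is not intended, the sentence in 4.1 is wrong. Loss could also be uneven: Protocol 1.4.2 reports application site pain in 4.4% on crisaborole against 1.2% on vehicle in the earlier controlled studies, generally early in treatment.

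The omission stands. The rest carries less weight. The documents do not link application site pain to missed assessments, and they give no sign that anyone was never reassessed. Being narrower than the protocol FAS breaks no protocol rule: Protocol 9 lets the SAP modify the plan and asks for an amendment only for major changes to the primary endpoint or its analysis. These endpoints are secondary, and Protocol 9.2.3 sets no missing-data rule for them. Requiring an all-FAS denominator would replace one acceptable convention with another and undo a restriction that the SAP wrote in.

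**Conclusion.** No change is needed. SAP 4.1 lacks one qualifier, and analysts can fill the gap sensibly by taking the timepoint as post-baseline and applying 5.3.1 to the subjects who remain. Counting the others as failures would also give a valid descriptive percentage.

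On the assumed counts, the choice moves a pooled crisaborole rate by 0.5 points (1 of 60) to 3.5 points (6 of 60), and a single-cohort rate by up to 3.7 points (3 of 30). It moves nothing if every dosed subject was seen again. These figures assume 40% enrolment spread as planned and response near the Phase 3 rates. The primary summary, percent change in EASI, uses observed data and is the same either way. Adding the qualifier and a count of excluded subjects to the responder tables would be harmless, but it is optional wording.
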